Appendix 4: Baseline Subject Questionnaire (page 1 of 1) **34**

Appendix 5: 1 Week Follow-Up Questionnaire **35**

Appendix 7: Before and After Laser Treatment Instructions **37**

Protocol Summary

Title	Open-label, Prospective, Multicenter Pivotal Study to Evaluate the Cutera enlighten Laser and a Micro-Lens Array Handpiece Attachment for the Treatment of Acne Scars
Objective	
a. To evaluate the safety of the Cutera enlighten laser with a Micro-Lens Array handpiece attachment in the improvement of acne scars.
 
b. To evaluate the efficacy of the Cutera enlighten laser with a Micro-Lens Array handpiece attachment in the improvement of acne scars.

Study Design	Open-label, Prospective, Multicenter Pivotal Study to Evaluate the Cutera enlighten multi-wavelength 532 nm and 1064 nm Nd:YAG picosecond duration laser with a Micro-Lens Array handpiece attachment for the Improvement of Moderate and Severe Acne Scars.
Enrollment	Approximately 45 subjects will be treated
Primary Endpoint	
 Correct identification of the 12 weeks post final treatment photographs from the baseline by at least two of the three blinded reviewers in 75% of the patients and an improvement of one point in the ASAS.
Safety Endpoint	
 Safety of the Cutera enlighten laser with a Micro-Lens Array handpiece attachment assessed by the frequency and severity of device related adverse events
Secondary Endpoints	
 [REDACTED] [REDACTED]
Exploratory Analysis	
 [REDACTED]
Subject Population	Female or male subjects, age 18 to 65 years, Fitzpatrick skin types I-VI
Planned Schedule	
First subject enrolled: August 2017
 
Last subject last visit: September 2018

1. PURPOSE

The purpose of this pivotal investigation is to evaluate the efficacy and safety of the Cutera enlighten multi-wavelength 532 nm and 1064 nm Nd:YAG picosecond pulse duration laser and an investigational micro-lens array (MLA) handpiece attachment for improvement of acne scars.

2. BACKGROUND INFORMATION

Affecting nearly 40 to 50 million people annually, acne is the most common skin condition in the United States.¹ Acne lesions typically begin to appear in puberty and persist throughout adolescence. Approximately 85% of people between the ages of 12 and 24 have experienced acne.² This wide spread skin condition predominantly affects teens and young adults, but can occur in older adults as well. Countless treatment modalities exist for acne sufferers, however even with effective treatment moderate and severe lesions can result in scarring. Post-acne scarring is estimated to occur in 95% of patients and is a common cosmetic concern for many patients.³ Furthermore, in some patient groups acne scarring is especially devastating and may be a risk factor for suicide.⁴

Scar formation occurs as a result of damage to the layers and substructures of the skin. Following injury to the skin from the acne infection and more severe lesions, a multi-stage healing process begins, which includes inflammation, proliferation and maturation. Unsightly scars result from an abnormal healing process. While the exact cause of abnormal skin healing is unknown, it is thought that excessive collagen and fibrotic tissue forms and a lack of elastic fibers contributes to tough, stiff, nodular scar tissue.⁵⁻⁶ Certain factors increase the likelihood of an abnormal skin healing process, such as patient age or racial/ethnic background, depth of injury and extent of infection.⁷⁻⁸

Acne scars are atrophic scars, with subtypes classified based on scar appearance and skin depth. Ice pick scars are narrow in width at the surface (<2mm) and typically taper in width as the scar extends vertically deep into the dermis. Box car scars are round or oval indentations in the skin surface, with well-defined edges, that may be shallow or deep. Rolling scars are atrophic scars that occur as a result of abnormal fibrous anchoring of the dermis to the subcutis and create a rolling or rippling appearance of the skin surface.⁹

Treatment modalities for acne scarring include ablative laser skin resurfacing, dermabrasion, chemical peels, or a combination of modalities.¹⁰ These traditional, highly effective treatment options are accompanied by undesirable side effects such as significant pain and post-procedure downtime. There is a demand for effective, noninvasive treatment methods for patients suffering from acne scars such as non-ablative laser and light-based therapy to devices that utilize radiofrequency waves.¹¹⁻¹³ Treatment with non-ablative, non-invasive devices cause heat production and heat-induced wound healing within the dermis that over time causes a cascade of cellular events leading to new collagen production.¹⁴⁻¹⁵ Dermal collagen remodeling leads to an improved texture and appearance of the skin, which should also improve the appearance of facial acne scars.

Histology of fractionated laser delivery has demonstrated the formation of vacuoles, or areas of laser induced optical breakdown (LIOB).¹⁶ LIOB occurs when the intensity of the pulse is sufficiently high to generate plasma. Plasma is caused by electrons being stripped from the target material. The resulting electrons continue to absorb the laser heat, creating a vapor plume which forms a cavitation bubble that is observed as an LIOB in histological preparations.

In 2012, Habbema et al., demonstrated that highly focused, fractionated 1064 nm picosecond pulses could create subsurface LIOBs in the upper dermis and 30 days post treatment, they showed new collagen in the areas of the LIOBs, a natural wound healing process as a response to this type of injury.¹⁷

Subsequently, picosecond lasers utilizing 755nm wavelength and a fractionated delivery system have been shown to improve the appearance of facial acne scars.¹⁸ Histological samples taken from the acne scar patients demonstrated improvements in the dermal elastic fibers, collagen and mucin. No severe side effects were observed and the patients tolerated the procedures without complications. The LIOBs observed in the facial acne study were located in the epidermis due to the higher absorption characteristics of 755nm in melanin as compared to 1064 nm used in Habbema's study.

Fractionated delivery of picosecond lasers on humans has been demonstrated to be safe. A similar device to MLA, utilizing 755nm wavelength and a fractionated delivery system, has obtained FDA 510K clearance (K143105) and has been shown to improve the appearance of facial acne scars.¹⁸

Recently, a holographic diffractive beam-splitter technology delivering fractionated picosecond 532 nm and 1064 nm wavelengths has also been described and is available commercially outside of the US (Syneron Candela), but to date, no FDA clearance exists for this device. The company reports the device is able to focus the LIOBs in the epidermis with the 532 nm wavelength and in the upper papillary dermis with the 1064 nm wavelength safely.¹⁹

[REDACTED]

[REDACTED]

[REDACTED]

[REDACTED]		
[REDACTED]	[REDACTED]	[REDACTED]

4. STUDY OBJECTIVES

The objectives of this pivotal study are:

- a. To evaluate the safety of the Cutera enlighten laser with a Micro-Lens Array handpiece attachment in the improvement of acne scars.
- b. To evaluate the efficacy of the Cutera enlighten laser with a Micro-Lens Array handpiece attachment in the improvement of acne scars.

5. STUDY DESIGN

This is an open-label, prospective, multicenter, pivotal study in up to 45 male or female subjects, age 18 to 65 years who desire laser treatment for the improvement of acne scars. Subjects will receive up to [REDACTED] apart with the Cutera enlighten laser with the Micro-Lens Array handpiece attachment. [REDACTED]

[REDACTED] Subjects will return to the site after all study treatments have been delivered for follow-up visits: [REDACTED] and 12 weeks [REDACTED] following their final study treatment.

5.1 Study Endpoints

5.1.1 Primary Efficacy Endpoint

The primary endpoint is correct identification of the 12 weeks post final treatment photographs from the baseline by at least two of the three blinded reviewers in 75% of the patients and an improvement of one point in the ASAS.

[REDACTED]

[REDACTED]

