11. DATA ANALYSIS PLAN

11.1 Sample Size

The primary objective is to show that the response rate (as defined below) is significantly greater than 50%. Under the assumption that the true population response rate is 75%, 40 subjects will provide 80% power to reject the primary hypothesis. To allow for up to a 10% dropout rate, 45 subjects will be treated.

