11.3.2 Primary Efficacy Analysis

The primary endpoint is a responder, where a clinical response is defined as at least two of the three blinded reviewers selecting the correct order of treatment with at least a one-point improvement in the ASAS from baseline to 12 weeks. The primary hypothesis is as follows:

$H_0: \Pi = 0.5$

vs.

$H_A: \Pi \neq 0.5$,

where Π is the population response rate. The primary analysis will place an exact two-sided 95% confidence interval around the observed response rate and compare the lower bound to 50%. If the lower bound exceeds 50% the primary hypothesis will be rejected in favor of the response rate being greater than 50%.

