13.4 Protocol Amendments

Neither the principal investigator nor the sponsor will modify or alter this protocol without first obtaining the concurrence of the other party (with the exception of amendments which involves mitigating a medical emergency or immediate health risk to the subject). The party initiating an amendment must confirm it clearly in writing and it must be signed and dated by the sponsor and the principal investigator. IRB approval must be obtained before implementation of an amendment.

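### The primary endpoint contains a 75%-of-patients threshold that the success rule (lower confidence bound above 50%) does not, and nothing visible says which governs

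*Combined protocol and SAP*

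**What the plan says.** The primary endpoint is described in four places.

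- **Section 5.1.1** requires correct identification of the 12-week photographs "by at least two of the three blinded reviewers in 75% of the patients and an improvement of one point in the ASAS".
- **The Protocol Summary**, in its primary endpoint row, carries the same threshold: "Correct identification of the 12 weeks post final treatment photographs from the baseline by at least two of the three blinded reviewers in 75" per cent of patients.
- **Section 11.3.2** defines a response subject by subject: "at least two of the three blinded reviewers selecting the correct order of treatment with at least a one-point improvement in the ASAS", measured from baseline to 12 weeks. It then gives the decision rule for the exact two-sided 95% interval: "If the lower bound exceeds 50% the primary hypothesis will be rejected in favor of the response rate being greater than 50" per cent. No 75% condition appears.
- **Section 11.1** agrees with 11.3.2 on the benchmark: "The primary objective is to show that the response rate (as defined below) is significantly greater than 50" per cent. Its only use of 75% is as a planning value: "Under the assumption that the true population response rate is 75" per cent, it says, 40 subjects give 80% power. It then treats 45 to allow for 10% dropout.

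No visible text says which statement takes precedence, or whether both must be met.

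**The concern.** This is an open-label pivotal study with one primary efficacy decision, so the pass mark should be the same wherever it is stated. A reader of the summary or 5.1.1 would hold the study to a different standard from a reader of 11.3.2.

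The 75% in 5.1.1 can be read in two ways:

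- **Reading A:** it is a minimum observed rate of composite responders.
- **Reading B (the literal grammar):** it is a minimum rate of correct photograph identification only. It is then a different quantity from the 75% in 11.1, which refers to the composite, and the ASAS clause has no study-level threshold.

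Under Reading A, a result of 28/40 (70%) is a success by 11.3.2 and a failure by 5.1.1. If the choice between them is left until the data are known, the prespecified rule no longer protects the conclusion. The power statement in 11.1 also concerns rejecting 50%; it does not cover reaching an observed 75%.

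**Working it through.** **Inputs.** Null rate 50%, assumed true composite rate 75%, 40 evaluable subjects, 45 treated, stated power 80% (all section 11.1). Exact two-sided 95% interval with lower bound compared to 50% (section 11.3.2). Observed threshold 75% (Protocol Summary and section 5.1.1). I take the exact interval to be Clopper-Pearson.

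**Step 1: smallest passing count under 11.3.2.** The lower bound for x of n is the 2.5% quantile of Beta(x, n − x + 1).

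- n = 40: 26/40 gives 0.483 (fails); 27/40 gives 0.509 (passes).
- n = 45: 29/45 gives 0.488 (fails); 30/45 gives 0.511 (passes).

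**Step 2: the plan's own power.** With X ~ Binomial(40, 0.75), P(X ≥ 27) = 0.8968. The stated 80% is not reproduced. The exact figure is higher, and normal approximations are higher again (91.7% with the null variance, 95.5% unpooled). The sample size is therefore not too small for the 11.3.2 rule; this is a separate matter. The dropout allowance does reproduce: 40/0.9 = 44.4, rounded up to 45.

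**Step 3: Reading A.** An observed 75% needs 0.75 × 40 = 30 of 40, or 0.75 × 45 = 33.75, so 34 of 45.

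| n | 11.3.2 passes from | 75% reached from | P(11.3.2 met) | P(75% reached) | P(rules disagree) |
|---|---|---|---|---|---|
| 40 | 27 | 30 | 0.8968 | 0.5839 | 0.8968 − 0.5839 = 0.3129 |
| 45 | 30 | 34 | 0.9247 | 0.5457 | 0.9247 − 0.5457 = 0.3790 |

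The rules disagree at 27–29 responders of 40, or 30–33 of 45. For P(X ≥ 30 of 40) to reach 0.80, the true rate would have to be about 0.791.

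**Step 4: Reading B, n = 40.** The documents give no identification rate p. It cannot be below 75% if the composite rate is 75%, because every composite responder has been correctly identified. I therefore take 75–100% as an assumed range. The model is I ~ Binomial(40, p) subjects identified and C given I ~ Binomial(I, 0.75/p) composite responders. The rules compared are I ≥ 30 and C ≥ 27. The ASAS clause of 5.1.1 is left out because it has no threshold to apply.

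| p | 11.3.2 met, identification missed | Identification met, 11.3.2 missed | Total |
|---|---|---|---|
| 0.75 | 0.3129 | 0 | 31.3% |
| 0.80 | 0.0784 | 0.0209 | 9.9% |
| 0.85 | 0.0069 | 0.0803 | 8.7% |
| 0.90 | 0.0001 | 0.1019 | 10.2% |
| 1.00 | 0 | 0.1032 | 10.3% |

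At p = 0.75 every disagreement is a pass on 11.3.2 with identification missed. From 0.85 upward it is mainly the reverse.

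**The case against.** The strongest reply is that there is only one decision rule. Section 11.3.2 alone gives hypotheses, an interval method and a rejection condition, and 11.1 independently names the same 50% benchmark. The 75% in 5.1.1 equals the planning rate in 11.1, so it may simply have been carried into the endpoint sentence. The Reading A figures support that view: requiring the observed rate to reach the assumed true rate succeeds only a little more than half the time (58.4% at n = 40, 54.6% at n = 45), an odd pass mark for a design said to have 80% power. This is persuasive about intent, and 11.3.2 probably does govern. It does not remove the conflict, because the summary and 5.1.1 place 75% inside the endpoint definition and no visible text calls it an assumption. If it is a carry-over, deleting it is the cure.

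A second reply is that redacted text may settle the matter. Text after the 5.1.1 sentence is blacked out, so the finding is limited to what can be read. The statements in 11.1 and 11.3.2 are legible, and neither sets a 75% criterion.

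A third concerns Reading B. Leaving out the ASAS clause makes the identification rule easier to meet. From about 90% identification, the 10% disagreement is essentially the ordinary failure probability of 11.3.2 (1 − 0.8968 = 0.1032). That stands as a limit on those figures: they illustrate a truncated rule. They do not measure the full 5.1.1 sentence, which cannot be evaluated until the ASAS clause is given a threshold.

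**Conclusion.** The concern holds and must be fixed. The visible plan contains two statements of primary success that differ in threshold and, on the literal reading, in the quantity measured. Under Reading A, at the plan's own true rate of 75%, they give opposite answers in 31.3% of studies with 40 evaluable subjects and 37.9% with 45. The chance of success with 40 is 89.7% under 11.3.2 and 58.4% under a 75% observed threshold. Reading B gives about 9% to 31% over the assumed identification range, with the ASAS clause omitted.

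These sizes rest on a Clopper-Pearson interval, independent subjects and a true composite rate of exactly 75%. The textual conflict does not depend on them. Power for the 11.3.2 rule is not in doubt.

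**What to change.** State one success rule and say what the 75% is. The rule consistent with section 11.1 is the one in 11.3.2, so the Protocol Summary and 5.1.1 could read:

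> The primary endpoint is the proportion of responders. A responder is a subject whose photograph pair is put in the right order by two or more of the three blinded readers and whose ASAS grade improves by one point or more between baseline and 12 weeks after the last treatment. The study succeeds if the exact two-sided 95% confidence interval for this proportion lies wholly above 50%.

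Remove the 75% from both places and keep it only in 11.1, labelled as the assumed composite rate. In the same edit, name whose ASAS score counts, since 5.3.1 and 5.3.2 give the scale to the blinded evaluators and to the Investigator. Report the identification rate and the ASAS responder rate separately, each with an exact interval.

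If the sponsor does intend 75% as a further threshold, 11.3.2 must say so and on which quantity, and 11.1 must restate the power. On the composite that is about 58% with 40 subjects at a true rate of 75%; 80% power would need a true rate of about 79%, so the design might have to be reconsidered.

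The recommended change costs one amendment signed by the sponsor and the principal investigator. Section 13.4 adds that "IRB approval must be obtained before implementation of an amendment". There are two extra descriptive lines in the primary results table, and no additional subjects or data.

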5.1.3 Safety Endpoints

- Safety of the Cutera enlighten laser with Micro-Lens Array handpiece attachment as assessed by the frequency and severity of device related adverse events.

[REDACTED]

[REDACTED]

5.2 Study Duration

[REDACTED]

The screening and first laser treatment may be combined into one visit provided that the subject has signed the IRB-approved Informed Consent Form prior to the commencement of any study-related procedures and has met all criteria to be enrolled in the study.

5.3 Study Effectiveness Assessments

5.3.1 Blinded Evaluators and Investigator's Global Assessment of Improvement

Blinded improvement assessments will be performed 12 weeks post the [REDACTED] or final laser treatment. Blinded Evaluators will be asked to assess the subject's before (baseline) and after photographs in one and/or both of the below methods:

- Determine the temporal order (before and after) of each photograph pair.

- Rate the degree of improvement observed from baseline using the Acne Scar Assessment Scale (ASAS)

A. Acne Scar Assessment Scale (ASAS): The ASAS is a static assessment scale that allows the Investigator to measure his/her impression of acne scar severity within the treatment area. The treatment area on each side of the face will be assessed separately, then will be averaged to obtain a global score.

Term	Grade	Description
Clear	1	No depressions are seen in the treatment area. Macular discoloration may be seen.
Very Mild	2	A single depression is easily noticeable with direct lighting (deep). Most or all of the depressions seen are only readily apparent with tangential lighting (shallow).
Mild	3	A few to several, but less than half of all the depressions are easily noticeable with direct lighting (deep). Most of the depressions seen are only readily apparent with tangential lighting (shallow).
Moderate	4	More than half of the depressions are apparent with direct lighting (deep).
Severe	5	All or almost all the lesions can be seen with direct lighting (deep).

□

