5.3.2 Investigator Assessments

[figure not shown]
At baseline, [REDACTED], the Investigator will assess the efficacy of the Cutera enlighten laser with the MLA handpiece attachment treatment using the ASAS, GAIS, and Skin Quality Rating Scale. Baseline photos of subjects may be used while assessing the ASAS, GAIS, and Skin Quality Rating Scale.

A. Acne Scar Assessment Scale (ASAS): The ASAS is a static assessment scale that allows the Investigator to measure his/her impression of acne scar severity within the treatment area. The treatment area on each side of the face will be assessed separately, then will be averaged to obtain a global score.

Term	Grade	Description
Clear	1	No depressions are seen in the treatment area. Macular discoloration may be seen.
Very Mild	2	A single depression is easily noticeable with direct lighting (deep). Most or all of the depressions seen are only readily apparent with tangential lighting (shallow).
Mild	3	A few to several, but less than half of all the depressions are easily noticeable with direct lighting (deep). Most of the depressions seen are only readily apparent with tangential lighting (shallow).
Moderate	4	More than half of the depressions are apparent with direct lighting (deep).
Severe	5	All or almost all the lesions can be seen with direct lighting (deep).

□

[REDACTED]	[REDACTED]

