7.4 Phone and Follow-Up Visits

There are [REDACTED] follow-up visits at [REDACTED] and 12 weeks [REDACTED] () following the final laser treatment.

The following procedures will be performed during the phone and follow-up visits:

1. Assessment of Concomitant Medications: Assess and record any additions, changes and/or deletions in prescription and nonprescription concomitant medications since the previous study visit.
2. Assess for any ongoing, previously reported, and/or new adverse events and expected adverse device effects.

During the follow-up visits:

1. Cleanse subject's treated area with a mild cleanser to remove any cosmetics, lotions, or perfumes.
2. Photographs of the treated area(s) will be taken at the same pre-defined angles (Section 5.5).
3. Investigator will assesses the efficacy of the Cutera enlighten laser with the Micro-Lens Array handpiece attachment treatment using the ASAS, [REDACTED]

8. ADVERSE EVENTS and ADVERSE DEVICE EFFECTS

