11.3 Statistical Analysis Methods

This is a study to evaluate safety and efficacy of the Cutera enlighten laser with the Micro-Lens Array handpiece attachment. Outcome measures will be assessed around multiple endpoints. These measures will be: degree of improvement as assessed by the Investigator, blinded evaluators, [REDACTED] and safety. Additional assessments may also be performed but are not considered part of the analysis (i.e. Subject post-treatment questionnaire).

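### The primary endpoint does not say whose ASAS score counts, and section 5.3.1 permits but does not require a blinded ASAS, so the open-label Investigator's score is not excluded

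*Combined protocol and SAP*

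**What the plan says.** Section 5.1.1 sets the primary endpoint as identification of the 12-week photographs "by at least two of the three blinded reviewers in 75% of the patients and an improvement of one point in the ASAS". The Protocol Summary repeats this. Section 11.3.2 turns it into a per-subject response: at least two of three blinded reviewers "selecting the correct order of treatment with at least a one-point improvement in the ASAS from baseline to 12 weeks". In each place the blinded reviewers are tied to the photograph order, and the ASAS condition follows without a named rater.

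Section 5.3.1 describes the blinded assessment at 12 weeks. Evaluators assess the "before (baseline) and after photographs in one and/or both of the below methods". The first method is to determine the order of the pair. The second is "Rate the degree of improvement observed from baseline using the Acne Scar Assessment Scale (ASAS". The scale is then described as static, and as a record of the Investigator's impression. For the scoring unit, "The treatment area on each side of the face will be assessed separately, then will be averaged to obtain a global score".

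Section 5.3.2 has the Investigator score the ASAS at baseline, and adds: "Baseline photos of subjects may be used while assessing the ASAS, GAIS, and Skin Quality Rating Scale". Section 7.4 repeats the score at the follow-up visits, which include 12 weeks: "Investigator will assesses the efficacy of the Cutera enlighten laser with the Micro-Lens Array handpiece attachment treatment using the ASAS". Section 11.3 lists "degree of improvement as assessed by the Investigator, blinded evaluators" among the outcome measures and assigns neither rater to the primary endpoint.

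**The concern.** This is a single-arm, open-label pivotal study, and blinded photograph review is its main protection against expectation bias. Response has two halves, and only the ordering half is clearly blinded. A team following the readable text could have the reviewers order the photographs and take the ASAS change from the Investigator, who knows the subject was treated and may have the baseline photographs in view. Among correctly ordered subjects, an unblinded score would then decide who is a responder. If the rater and the rule for combining grades are not fixed in advance, they could also be chosen after the data are seen.

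A smaller issue remains even if the reviewers' own ASAS is meant. Section 5.3.1 asks for improvement from baseline on a scale it calls static. A reviewer who has just ordered the pair has a belief about which photograph is baseline, and that belief could influence the grade.

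**Working it through.** **The text, side by side**

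| Place | Photograph order | ASAS |
|---|---|---|
| Protocol Summary, 5.1.1 | blinded reviewers, two of three | rater not named |
| 11.3.2 | blinded reviewers, two of three | rater not named; may attach to the reviewers |
| 5.3.1 | one of two blinded methods | the other blinded method; one or both may be used |
| 5.3.2, 7.4 | none | Investigator, at baseline and follow-up |
| 11.3 | not mentioned | improvement by Investigator and by blinded evaluators, neither marked as primary |

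A blinded ASAS is thus permitted but not guaranteed, and the Investigator's ASAS is scheduled at the visits that matter.

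**The success rule.** Section 11.3.2 requires the lower limit of an exact two-sided 95% interval to exceed 50%. At n=40 (section 11.1), 26/40 gives 48.3% and 27/40 gives 50.9%, so 27 responders are needed. At n=45, 29/45 gives 48.8% and 30/45 gives 51.0%, so 30 are needed.

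**The plan's own figure.** Section 11.1 states 80% power with 40 subjects at a 75% response rate. The exact rule gives P(X ≥ 27 | n=40, p=0.75) = 0.897. The stated figure is conservative, and the difference does not affect this point. The dropout allowance reproduces: 40/0.9 = 44.4, rounded up to 45.

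**How far the blinded order test protects.** If the photographs are indistinguishable and the three reviewers guess independently, a majority is right with probability 3 × 0.5³ + 0.5³ = 0.50. Response also needs an ASAS gain, so the response rate cannot exceed 0.50. P(X ≥ 27 | n=40, p=0.50) = 0.0192, and P(X ≥ 30 | n=45, p=0.50) = 0.0178. These are ceilings, whoever scores the ASAS.

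**Where order is identifiable (illustration).** The documents give neither the component rates nor any size of rater inflation, so both are assumed. Let A be the proportion correctly ordered and d the inflation of the ASAS gain rate among them. With the true composite rate at the null, the observed rate is p = 0.50 + A × d.

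| d | A | p | P(success), n=40 | P(success), n=45 |
|---|---|---|---|---|
| 0 | any | 0.500 | 1.9% | 1.8% |
| 0.05 | 0.75 | 0.5375 | 5.5% | 5.5% |
| 0.05 | 0.90 | 0.545 | 6.7% | 6.7% |
| 0.10 | 0.75 | 0.575 | 13% | 14% |
| 0.10 | 0.90 | 0.590 | 18% | 19% |

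A 10-point inflation adds 40 × 0.75 × 0.10 = 3.0 to 40 × 0.90 × 0.10 = 3.6 responders among 40.

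**The case against.** The best defence is that a blinded ASAS is what the plan means. Section 5.3.1 lists exactly two blinded methods at 12 weeks, and they are the two halves of the primary endpoint. Section 11.3.2 joins them in one clause, so two of three can govern both conditions and would itself supply the combining rule. Taken literally, the either-or-both wording would make ordering optional too, although the endpoint cannot do without ordering. It may simply be loose drafting. In addition, text directly after 5.1.1, the secondary endpoints, and parts of 5.3.2 and 7.4 are blacked out in the public copy and could name the rater.

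All of this stands as a possible reading. It does not make a blinded ASAS mandatory or rule out the Investigator's score, and it leaves the rating of improvement from baseline in place.

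A reader might infer that the plan uses an unblinded primary score, or that it has no way to combine three reviewers' grades. The documents support neither inference: the first is only not excluded, and the second fails if two of three covers both conditions. Nor are 13% to 18% estimates of this trial's false-success rate, because they rest wholly on an assumed inflation.

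**Conclusion.** The concern holds as a gap in specification: the readable text does not fix whose ASAS defines response, and it lets blinded evaluators omit that score. The exposure is real but bounded. An unblinded ASAS cannot create responders among subjects whose photographs were not correctly ordered, and with guessed order success stays at or below about 1.9% at n=40. It matters where the order is identifiable but the change is near one ASAS grade, because rater leniency then decides response. The size there is unknown. It is zero without inflation; the 10-point illustration assumes a true composite rate of 50% and correct order in 75% to 90% of subjects. If the reviewers' ASAS is the intended score, most of the exposure goes, but not all, since the reviewer may believe they know which photograph is baseline. Confidence is medium because blacked-out text may settle the rater. This is a cheap improvement, not a fatal flaw.

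**What to change.** - In 5.3.1, replace the either-or-both wording with a requirement that the three planned blinded reviewers do both tasks for the primary endpoint. They should grade each baseline and 12-week photograph set on the static ASAS without knowing the visit, with the change computed afterwards.
- In the Protocol Summary, 5.1.1 and 11.3.2, state that this blinded ASAS defines response and that at least two of three reviewers must show the one-point gain. Say whether the same two must also have ordered the pair correctly.
- In 5.3.1, amend the ASAS definition so that it refers to the blinded evaluator.
- Keep the Investigator's live ASAS as supportive.
- If blacked-out text already names the rater, make these sections consistent with it.

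**Cost.** The change needs wording in four places and a reader form; the reviewers and photographs are already planned. The workload is at most 45 × 2 = 90 photograph sets per reviewer. With each side of the face graded separately, that is 180 grades per reviewer and 540 for three.

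**Downside.** Photograph grading may be less sensitive than live grading and could lower the observed response rate. ASAS grades 2 and 3 refer to tangential light, while section 5.5 asks only that lighting be adequate and consistent. The wording can be settled before any 12-week reading, but any change to photographic lighting would have to be set before baseline photographs are taken. The document is dated 17 July 2017 and plans first enrolment for August 2017, so on that timetable the interval is short.
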